5.6 Statistical Tests and Adjustment for Multiplicity

Results of statistical analyses are considered significant if the p-value from the statistical test is < 0.05 for two-sided tests and < 0.025 for one-sided tests.

Since all analyses in this study are considered exploratory, no adjustments for multiple comparisons will be made.

5.7 Software for Analyses

Statistical analyses will be performed using SAS version 9.4 or higher, or R v3.6.1 or higher. All tables, listings and figures presented in the analysis will be created using SAS version 9.4 or higher, or R v3.6.1 or higher.

6.0 PARTICIPANT DISPOSITION

Overall participant disposition including the number of participants screened, failed screening, enrolled, received at least one dose of IP, received IP through treatment completion visit, discontinued IP early, terminated early from the study and completed study will be summarized by cohort and overall. Reasons for early treatment and study discontinuation will also be summarized (Table 1). This table will be based on the screened population. A consort diagram showing participant flow will also be included as shown in Figure 1.

7.0 PARTICIPANT CHARACTERISTICS

These presentations will be based on the enrolled population.

7.1 Participant Demographics

Demographic data including baseline age, gender, race and ethnicity will be summarized by cohort and overall as in Table 2 and presented by participant. The listing will also include study registration date and indicate the eye determined to be the study eye.

7.2 Medical, Medication, Smoking and Ocular History

Medical, medication and smoking history and history of ophthalmic procedures will be summarized by cohort and overall (Tables 3 and 4, respectively) and presented by participant.

8.0 PARTICIPANT COMPLIANCE

These presentations will be based on the enrolled population.

8.1 Protocol Deviations and Unanticipated Problems

The total number of protocol deviations and unanticipated problems and the number and percentage of participants with deviations and unanticipated problems will be summarized by cohort and overall.

Effective July 1, 2019, with the implementation of National Institutes of Health (NIH) Intramural Research Program Policy 801, protocol deviations and unanticipated problems are classified by the Investigator as major or minor at the time of data entry (as opposed to serious or not serious), and seriousness of major deviations and unanticipated problems is determined after review by the NIH Institutional Review Board (IRB). The number of events per participant and the type (minor, serious, not serious, or pending determination by IRB) and outcome of events will also be summarized (Table 5). Listings of participant-specific and non-participant-specific protocol deviations and unanticipated problems will be presented.

8.1.1 IP Compliance Deviations

The number of expected doses, number of doses taken, number of doses missed, and the compliance rate will be summarized by participant, cohort, and overall as in Table 6.

For cohort 1, each dose consists of two pills of 8,000 IU of vitamin A palmitate, taken once per day, for a total of 16,000 IU per day. For cohort 2, each dose consists of three pills of 8,000 IU of vitamin A palmitate, taken twice per day, for a total of 48,000 IU per day.

For each participant, the number of expected doses will be calculated as follows:

$$N_{\text{doses expected}} = (\text{Date}_{\text{Month x/ early IP withdrawal}} - \text{Date}_{\text{IP first taken}}) * \text{Number of doses per day}$$

If participants took IP on the date they withdrew from the study or completed the study, the number of expected doses overall and between visits will be calculated as follows:

$$N_{\text{doses expected}} = (\text{Date}_{\text{Month x/ early IP withdrawal}} - \text{Date}_{\text{IP first taken}} + 1) * \text{Number of doses per day}$$

Where: Month x = Month 2 for Cohort 1 and Month 1 for Cohort 2

$\text{Date}_{\text{IP first taken}}$ = date of the visit when IP was first dispensed to the participant

Number of doses per day = 1 for Cohort 1 and 2 for Cohort 2

The number of pills returned at each study visit will be recorded by the site. Number of doses taken and missed will be calculated for each period timeframe as follows:

$$N_{\text{doses taken}} = (N_{\text{pills dispensed}} - N_{\text{pills returned}}) / \text{Number of pills per dose}$$

$$N_{\text{doses missed}} = N_{\text{doses expected}} - N_{\text{doses taken}}$$

Where: Number of pills per dose = 2 for Cohort 1 and 3 for Cohort 2.

Compliance rate will be calculated as follows:

$$\text{Compliance Rate} = (N_{\text{doses taken}} / N_{\text{doses expected}}) * 100$$

Participants are considered to have complied with the protocol if they consumed at least 80% of the total expected doses of vitamin A palmitate. Compliance rates falling below 80% will be highlighted in yellow in Table 6.

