Design: This is a prospective, uncontrolled, single center, pilot study to investigate the potential efficacy and safety of vitamin A palmitate dosing in improving dark adaptation in participants with AMD and abnormal dark adaptation. Participants in the first cohort were instructed to take 16,000 IU of vitamin A palmitate daily for two months. Enrollment for Cohort 1 ended on May 24, 2019. Participants in the second cohort will be instructed to take 48,000 IU of vitamin A palmitate daily for one month. Participants in both cohorts will continue in the study for one month after ending Vitamin A supplementation. Participants in Cohort 1 may enroll into Cohort 2 as long as their last intake of vitamin A palmitate was greater than two months prior to their enrollment into Cohort 2.

Outcome Measures: For each cohort, the primary outcome is the measurement of dark adaptation parameters (thresholds and kinetics) by the following: dark adaptation times as measured by the AdaptDx comparing before and after vitamin A palmitate supplementation and dark adaptation parameters as measured by the Medmont comparing before and after vitamin A palmitate supplementation. The primary outcome will be assessed at Month 2 in the first cohort and Month 1 in the second cohort. For both cohorts, the secondary outcomes include changes in low luminance visual acuity (LLVA) and changes in patient reported outcomes as measured by the low luminance questionnaire (LLQ). The secondary outcomes also include measurement of dark adaptation parameters (thresholds and kinetics) comparing baseline and one month after completing supplementation (Month 3 in Cohort 1 and Month 2 in Cohort 2).

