4.4.2 Dosage, Administration, and Storage

For both cohorts, participants are considered to have complied with the protocol if they have consumed at least 80% of the total doses over the treatment period. The first cohort was instructed to take two 8,000 IU pills by mouth once per day (16,000 IU) with a meal. The preliminary analysis of the data from the first cohort shows that 16,000 IU of vitamin A palmitate per day was well tolerated with no adverse events requiring discontinuation of the study product. The data also show that the first cohort did not present significant improvement in dark adaptation after taking 16,000 IU of vitamin A palmitate per day. A higher dose (50,000 IU) has been previously used in other studies of monogenic (inherited) retinal degeneration with good effect and good tolerance.²⁶ It has even been explored in the context of individuals ≥ 50 years old with AMD, albeit a different study design, but the higher dose of vitamin A was well-tolerated.¹⁶ Therefore, for the second cohort, administration of three 8,000 IU pills will occur by mouth twice per day (48,000 IU) and should be taken with a meal. The vitamin A palmitate supplement should be stored at room temperature (15-30°C).

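### SAP 8.1.1 stops counting expected doses at early withdrawal, so an early stopper can score 100% compliance; Cohort 2's late-visit rule is also undefined

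*SAP*

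**What the plan says.** Protocol 4.4.2 treats participants in both cohorts as compliant if they have "consumed at least 80% of the total doses over the treatment period". SAP 8.1.1 words it as "Participants are considered to have complied with the protocol if they consumed at least 80% of the total expected doses of vitamin A palmitate" and then defines expected doses by formula. The count starts at the "date of the visit when IP was first dispensed to the participant" and ends at "Month x/ early IP withdrawal", where "Month x = Month 2 for Cohort 1 and Month 1 for Cohort 2". The difference in days is multiplied by doses per day: "Number of doses per day = 1 for Cohort 1 and 2 for Cohort 2". One day is added if the product was taken on the day the participant withdrew from or completed the study. Doses taken are pills dispensed minus pills returned, divided by pills per dose: "Number of pills per dose = 2 for Cohort 1 and 3 for Cohort 2".

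Table 6 reports expected, taken and missed doses and the rate for each participant, with cohort and overall totals. Rates below 80% are highlighted, and a footnote attributes that threshold to the protocol. Under SAP 8.0 the table uses the enrolled population, so early stoppers appear in it.

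The course is described in two ways. The protocol précis says: "Participants in the second cohort will be instructed to take 48,000 IU of vitamin A palmitate daily for one month", and Protocol 4.3 also gives one month. SAP 3.1 runs Cohort 2 dosing from baseline through the Month 1 visit. Protocol 4.3 and Appendix 2 put that visit at day 30, plus or minus 14 days.

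**The concern.** A compliance rate is read as the share of the intended treatment that was taken. If the denominator shrinks to the days a person stayed on the product, anyone who takes every dose until stopping scores 100%, however early the stop. Table 6 would then class that person as meeting a protocol rule that is stated over the treatment period.

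Such participants are foreseeable. SAP 5.1 allows up to ten in Cohort 2 to obtain five for the primary analysis, and Protocol 4.3 removes those who cannot tolerate the dose. The cohort total in Table 6 would be raised in the same way.

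The denominator can also grow. If the count runs to the actual visit, a late but in-window Month 1 visit adds expected doses beyond day 30. Whether those doses were really expected depends on which description of the course applies. For those days the flag has no settled meaning.

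**Working it through.** The documents contain no worked compliance figure to reproduce. The dosing inputs agree with each other: 2 × 8,000 × 1 = 16,000 IU per day and 3 × 8,000 × 2 = 48,000 IU per day.

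**Inputs.** Doses per day, 1 (Cohort 1) and 2 (Cohort 2), from SAP 8.1.1. Target days 30 and 60 and the 14-day window, from Protocol Appendix 2, so Month 1 falls on days 16 to 44 and Month 2 on days 46 to 74. *Assumption:* one month is 30 days, with 28 and 31 as a range.

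**Formulas.** Expected = (end day − start day) × doses per day. Rate = taken / expected × 100. Flag if the rate is below 80%.

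**1. Stop on day 10, every dose taken, remaining pills returned**
- Cohort 2, SAP formula: expected 10 × 2 = 20, rate 20/20 = 100%. With the added day: 22/22 = 100%.
- Cohort 2, 30-day course: 20/60 = 33.3%. With a 28- or 31-day month: 20/56 = 35.7% or 20/62 = 32.3%.
- Cohort 2, course ending at any in-window Month 1 visit: from 20/32 = 62.5% (day 16) to 20/88 = 22.7% (day 44).
- Cohort 1, SAP formula: 10/10 = 100%. Against 60 days: 10/60 = 16.7%. Against any in-window Month 2 visit: from 10/46 = 21.7% to 10/74 = 13.5%.

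On either description of the course this person is below 80%. Under the SAP formula the same person is at 100%. On a 30-day course the threshold is 0.8 × 60 = 48 doses, or 48/2 = 24 days, so any fully adherent Cohort 2 participant who stops before day 24 is classed differently by the two denominators.

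**2. Effect on the cohort total (assumed mix, for illustration)**
Take five Cohort 2 completers with 60 doses each and five who stop on day 10 with 20 each. Doses taken: 300 + 100 = 400. SAP total: 400/400 = 100%. Against 10 × 60 = 600 planned doses: 400/600 = 66.7%.

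**3. Exactly 30 days taken (60 doses) in Cohort 2, end date = actual visit**
- Day 30: 60/60 = 100%
- Day 37: 60/74 = 81.1%, not flagged
- Day 38: 60/76 = 78.9%, flagged
- Day 44: 60/88 = 68.2%, flagged

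If a month is 28 or 31 days, the first flagged day is 36 or 39, and the day-44 rate is 56/88 = 63.6% or 62/88 = 70.5%. In Cohort 1, 60 daily doses with the latest in-window visit give 60/74 = 81.1%, so there is no flag.

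**4. The added-day rule**
It applies on the date the study was completed. SAP 4.0 places the final study visit one month after treatment completion. Read literally, the rule misses a participant who takes a dose on the day of the treatment completion visit.

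**The case against.** The strongest reply is that the SAP separates two questions: adherence while on the product (Table 6) and persistence (Table 1 and the section 8.2 listing of withdrawals with reasons). Not counting doses after a documented withdrawal as missed is a recognised convention, and a person told to stop is not expected to go on dosing. This stands as a reason to keep the on-treatment rate. It does not justify applying the protocol's 80% rule to that rate. The protocol also treats one month as a course to be received: its replacement rule in section 3.0 turns on withdrawal before one month of supplementation.

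A second reply is that, under SAP 3.1, treatment runs to the visit. On that reading 32/32 at a day-16 visit is right, and 60/88 at day 44 records doses that really were missed. This stands. The late-visit flag is an error only if dosing ends at 30 days and Month x is the actual visit. The SAP does not say which date is meant. Its start date is a visit date and pills are counted at visits, so the actual date is the natural inference, but a target date would remove the problem.

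A reader might also infer that Table 6 is the trial's only record of exposure. It is not. Table 1 reports early discontinuation and receipt of product through treatment completion, serum vitamin A is measured at follow-up visits, and Table 6 itself prints doses taken, so 20 doses would be visible beside about 60.

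**Conclusion.** The point holds, with limited reach. The early-stopper result follows directly from the formula, assuming full dosing up to withdrawal and return of unused pills: a day-10 stopper scores 100% in either cohort, against 33.3% (Cohort 2) or 16.7% (Cohort 1) of a course to the target day. The late-visit result is conditional and concerns Cohort 2 only, for in-window visits on days 38 to 44.

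The consequence is confined to the rates, totals and highlighting in Table 6. A reader might infer that the efficacy analysis is affected. The documents do not support that: the 80% rule defines no population, and SAP 5.2 limits the primary analysis population to participants who receive the product through the treatment completion visit, so a day-10 stopper is not in it. Nor is every late attender flagged, as the Cohort 1 result and the day-37 result show.

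It would also go too far to conclude that 60 doses is the correct denominator for everyone. That would settle a course length the documents state in two ways. It would also flag participants who took every dose up to an early in-window visit: 32/60 = 53.3% at day 16 in Cohort 2 and 46/60 = 76.7% at day 46 in Cohort 1.

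**What to change.** 1. Reconcile the one-month course in Protocol 4.3 with dosing through the Month 1 visit in SAP 3.1. Which of them applies is for the sponsor to settle.
2. State in SAP 8.1.1 whether the Month x date is the actual visit date or the target date. If the course is tied to the visit, also state which end date applies to someone who stops and has no such visit.
3. Then apply the 80% flag to the doses of the full planned course so defined, including for participants who stop early.
4. Keep the current on-treatment rate as a second column of Table 6, labelled as such.
5. In the added-day rule, refer to completion of treatment rather than of the study.

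No new data are needed. The cost is a wording change, one more column in Table 6, and compliance figures that may look less favourable.

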8.1.2 Study Procedure Deviations

Table 7 will present the expected number of procedures and number and percentage of procedures missed by participant, cohort, procedure, and cumulatively across all participants. Number of procedures missed is defined when the site reports a missed procedure or when the protocol monitors note missed procedures at the site and will be presented as a sum. Expected number of procedures is defined based on the study flowsheet and will also be presented as a sum. Percentage of procedures missed will be calculated as follows:

$$\%_{\text{procedures missed}} = (N_{\text{procedures missed}} / N_{\text{expected procedures}}) * 100$$

8.1.3 Visit Schedule Deviations

The number of expected visits, number and percentage of missed visits, and number and percentage of out of window visits will be summarized by participant, cohort and cumulatively across all participants as in Table 8. Number of expected, missed and out of window visits will be presented as sums. The percentage of missed and out of window study visits will be calculated as follows:

$$\%_{\text{missed visits}} = (N_{\text{missed visits}} / N_{\text{expected visits}}) * 100$$

$$\%_{\text{out of window visits}} = (N_{\text{out of window visits}} / N_{\text{expected visits}}) * 100$$

8.2 Premature Treatment and Study Withdrawals

Participants who withdrew from treatment and study early will be summarized as outlined in Section 6.0 and listed separately along with reason(s) for withdrawal.

9.0 PRIMARY OUTCOMES ANALYSIS

The analysis of primary outcome will be considered exploratory; no adjustment for multiplicity will be performed. These analyses will be based on the primary analysis population.

9.1 Dark Adaptation Times

Change in RIT, as measured by the AdaptDx, from baseline in the study eye at treatment completion visit will be summarized (Table 9) and listed (Listing 1) for each cohort.

For each cohort, the mean change in RIT in the study eye at the treatment completion visit from baseline will be assessed using a Student's paired t-test (TTEST procedure in SAS) (Table 9).

The following hypothesis will be tested at a type I error rate of 5%, where $\mu_{\text{Baseline RIT}}$ is the mean RIT at baseline and $\mu_{\text{treatment completion RIT}}$ is the mean RIT at at the treatment completion visit:

$$H_0: \mu_{\text{Baseline RIT}} = \mu_{\text{treatment completion RIT}}$$

$$H_A: \mu_{\text{Baseline RIT}} \neq \mu_{\text{treatment completion RIT}}$$

9.2 Dark Adaptation Parameters

Changes in AdaptDx curve parameters measured at baseline and at treatment completion will be assessed by first fitting a two part (exponential and linear) curve to the data:

$$y = ae^{-bx} + c \max(x-d, 0) + e,$$

where y is the threshold, b is the cone adaptation rate, x is time after cessation of bleach, c is the rod slope, d is the time of the rod cone break, and $a + e$ is the cone-rod plateau. Changes in pre-bleach thresholds and kinetic parameters as measured by the Medmont in the study eye at the treatment completion visit will be compared to baseline for each cohort, as described in Flynn et. al.¹⁸ All dark adaptation parameters will be analyzed by researchers at the NEI.

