2.0 DATA SOURCE

Data will be received from the National Eye Institute (NEI) via their electronic data capture system (Electronic Medical Record, EMR), which will then be uploaded daily to the Coordinating Center's (CC) database, Advantage eClinical®. Medmont and AdaptDx kinetic measures (i.e., curve parameters) and Medmont pre-bleach thresholds will be collected and analyzed at the NEI and will not be entered into EMR or transferred to the CC. All other analyses described in this document will be performed by the CC.

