3.4 Outcomes

3.4.1 Primary Study Outcome

The primary outcome for the first cohort is the measurement of dark adaptation parameters (thresholds and kinetics) in the study eye by the following:

- Dark adaptation times and kinetic parameters (i.e., curve parameters) as measured by the AdaptDx comparing baseline and two months after vitamin A palmitate supplementation.
- Dark adaptation parameters (kinetic/curve parameters and pre-bleach thresholds) as measured by the Medmont comparing baseline and two months after vitamin A palmitate supplementation.

The primary outcome for the second cohort is the measurement of dark adaptation parameters (thresholds and kinetics) in the study eye by the following:

- Dark adaptation times and kinetic parameters (i.e., curve parameters) as measured by the AdaptDx comparing baseline and one month after vitamin A palmitate supplementation.
- Dark adaptation parameters (kinetic/curve parameters and pre-bleach thresholds) as measured by the Medmont comparing baseline and one month after vitamin A palmitate supplementation.

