10.4 Dark Adaptation Parameters

A similar analysis to the primary outcome analysis for dark adaptation parameters described in Section 9.2 will be conducted comparing baseline to post-treatment follow-up visit in each cohort. All dark adaptation parameters will be analyzed by researchers at the NEI.

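### SAP 9.2 calls a + e the cone-rod plateau, but in the printed curve a + e is the threshold at bleach offset

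*SAP*

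**What the plan says.** SAP 9.2 says of the AdaptDx data: "Changes in AdaptDx curve parameters measured at baseline and at treatment completion will be assessed by first fitting a two part" curve, described as exponential and linear. The equation is printed as "y = ae^{-bx} + c \max(x-d, 0) + e". The text makes y the threshold, b the cone adaptation rate, c the rod slope and d the time of the rod-cone break. It also states that "x is time after cessation of bleach" and that "a + e$ is the cone-rod plateau".

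The parameters matter because SAP 3.4.1 lists "Dark adaptation times and kinetic parameters (i.e., curve parameters) as measured by the AdaptDx" in the primary outcome for both cohorts. SAP 10.4 carries the method to the post-treatment follow-up visit as a secondary outcome: "A similar analysis to the primary outcome analysis for dark adaptation parameters described in Section 9.2".

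On responsibility for the analysis, SAP 2.0 says: "Medmont and AdaptDx kinetic measures (i.e., curve parameters) and Medmont pre-bleach thresholds will be collected and analyzed at the NEI". It adds that these measures do not go to the Coordinating Center.

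**The concern.** The equation and the label describe different points on the curve. A plateau is where the cone limb flattens before the rods take over. The sum a + e is where the limb starts, at its steepest point (the slope at x = 0 is -ab).

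An analyst who follows the sentence as written would report the extrapolated starting threshold as the plateau. Its change from baseline would then mix any change, or any fitting error, in a with the real change in the plateau.

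Little else in the documents would catch this. The plateau is mentioned only in SAP 9.2. The dark adaptation shells (Tables 9 and 15, Listing 1) report rod intercept time only. The code-validation records described in SAP 16.0 are held at the Coordinating Center, which does not receive these measurements. With five participants per cohort intended for the primary analysis (SAP 5.1), and Protocol 9.1 making the analysis mainly descriptive and participant by participant, a mislabelled individual value would be read directly.

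**Working it through.** **Inputs from SAP 9.2.** The curve is `y(x) = a·exp(-bx) + c·max(x-d, 0) + e`. Here exp() replaces the printed base e, because the SAP uses the letter e both for the base and for a parameter. I take b > 0 and d > 0, as an adaptation rate and a break after bleach offset imply.

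**Evaluating the printed curve**

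- Bleach offset, x = 0: `y(0) = a·1 + c·0 + e = a + e`.
- Cone limb, 0 ≤ x ≤ d: the rod term is zero, so `y = a·exp(-bx) + e`, which tends to e.
- Rod-cone break, x = d: `y(d) = e + a·exp(-bd)`.

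The plateau is therefore e (the asymptote) or `e + a·exp(-bd)` (the value at the break). Neither equals a + e unless a, b or d is zero, and each of those cases removes the cone limb or the break. The sign of a makes no difference.

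**Error in the level.** `(a + e) - y(d) = a·(1 - exp(-bd))`. The documents give no values for a, b, d or e, so these are assumptions:

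| b (per min) | d (min) | exp(-bd) | Error as share of a |
|---|---|---|---|
| 0.3 | 8 | 0.0907 | 91% |
| 0.5 | 12 | 0.0025 | 99.8% |
| 1.0 | 16 | about 1e-7 | 100% |

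A slower rate of b = 0.2 with d = 8 gives 80%.

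**Error in the change from baseline.** If a, b and d are the same at both visits, `a·(1 - exp(-bd))` cancels and the error is zero. If a moves, the error is roughly the shift in a. For illustration, assume a baseline of a = 2, b = 0.5, d = 12, e = -2, so that a + e = 0.000 and y(12) = -1.995:

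| Follow-up values | a + e | Change in a + e | y(12) | Change in y(12) |
|---|---|---|---|---|
| a = 2.3, e = -2.3 | 0.000 | 0.000 | -2.294 | -0.299 |
| a = 1.7, e = -2.0 | -0.300 | -0.300 | -1.996 | -0.001 |

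In the first row the label hides a real fall in the plateau. In the second it shows a fall that did not happen.

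**A form for which the label would be right.** With `a·(1 - exp(-bx)) + e` as the cone limb, the limit is a + e. This equals `(a + e) - a·exp(-bx)`, so it is the same family of curves with the constants renamed: the coefficient of the exponential changes sign and the constant term becomes a + e. The documents do not show whether the label or the equation is the slip.

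**The case against.** The algebra is not in dispute. The case on the other side is about weight.

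- **One descriptive clause.** No hypothesis, test, decision rule, table or listing uses the plateau. SAP 3.4.1 names curve parameters in general, and the AdaptDx bullets in Protocol 8.1 mention only dark adaptation times. This is fair, but SAP 9.2 lists the plateau beside b, c and d as one of the four quantities it interprets, so reading it as a reported parameter is natural.
- **Harm is conditional.** The NEI analysts may already use the right term, and all five coefficients are available under either label. This stands. Nothing in the documents shows which will be reported.
- **The sizes are illustrative.** The parameter values are assumed, and the two change-score examples use chosen shifts. This also stands: the supported range for the change runs from no error to an unknown amount.
- **It is naming only.** The alternative form describes the same curves. True, and that makes the fix cheap. It does not make the sentence right, because the label decides which number is called the plateau.
- **The text was read from PDF by a program.** An extraction fault cannot be excluded, but the equation is well formed and matches the description of an exponential and a linear part. The paper cited in SAP 9.2 is tied there to the Medmont analysis.

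**Conclusion.** The concern holds. For the curve printed in SAP 9.2, a + e is the threshold at bleach offset, not the cone-rod plateau. This needs only b > 0 and d > 0.

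The practical size is unknown. Under the main assumed range (b = 0.3 to 1.0 per minute, d = 8 to 16 minutes), the level would be off by 91% to 100% of a. The change from baseline would be off by about the shift in a, which is nothing if a, b and d are stable.

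The problem is confined to whatever is reported as the plateau. The fitted curve, b, c, d, the paired t-test on rod intercept time and the Medmont analysis do not depend on it, and SAP 5.0 makes every analysis exploratory. It should still be corrected, because this is the documents' only definition of a quantity among the primary-outcome curve parameters, and following it as written gives the wrong number.

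**What to change.** Reconcile the equation and the label in SAP 9.2; SAP 10.4 then follows by reference. There are two ways:

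1. Keep the printed equation. Define the cone-rod plateau as e, or as `e + a·exp(-bd)` if the value at the break is meant, and describe a + e as the threshold at bleach offset.
2. If another form was intended, such as `a·(1 - exp(-bx))` for the cone limb, print that equation and keep the label.

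In either case, compute the change in plateau from the corrected term. Using a different letter for the constant, or writing exp(), would remove the double use of e.

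The cost is one line of SAP text and no new data. No refitting is needed if the printed equation is the one used. If the alternative form was used, the coefficients convert by the renaming shown above.
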